Alternative Hypothesis (H1):

There is a significant difference in the reduction of Demodex mite count among patients with Demodex Blepharitis treated with at least one of the following therapies: Low Level Light Therapy (LLLT), Intense Pulse Light Therapy (IPL), Combined LLLT + IPL, greater than Mechanical with pharmacological Treatment.

[figure not shown]
Hypotheses

- LLLT or IPL, will be equally effective in reducing Demodex mite count and improving ocular surface parameters.
- IPL + LLLT will be more effective than LLLT or IPL alone in reducing Demodex mite count and improving ocular surface parameters.

7. Keywords

Demodex blepharitis, MGD, LLLT, IPL, Demodex mite count, Demodex mite eradication, Ocular surface parameters

Conceptual framework

Variables

Independent variables:

the different treatment modalities:

- 1.Low Level Light Therapy (LLLT)
- 2.Intense Pulse Light Therapy (IPL)
- 3.Combined LLLT + IPL
- 4.Mechanical with pharmacological treatment

Dependent variables: Mean Demodex Count, MGD Staging, OSDI Questionnaire, Meibum Quality, Meibum Expressibility, Telangiectasia Grading (0-3), Surface Staining (NEI Grading System), % Meibomian Gland Loss (MGL), Lipid Layer Thickness, Noninvasive Break-Up Time (NIBUT), Tear Meniscus Height (TMH),

8. Research Design

Single Center, 2x2 Factorial Randomized Control Trials

9. Research Methodology

Target Population: Demodex blepharitis patients at the Department of Ophthalmology, King Chulalongkorn Memorial Hospital.

This is a single-center, prospective, 2x2 factorial Randomized Control Trials involving outpatients with Demodex blepharitis presenting at the Department of Ophthalmology, King Chulalongkorn Memorial Hospital (KCMH) from Nov 2024 to Nov 2025.

The approach to participants: involves patients under the care of the research physician. They are recruited through advertisements and contacted through the patient's physician to introduce the researcher and seek volunteer participation.

The inclusion criteria consist of:

1. All patients who received a definite diagnosis of demodex blepharitis based on cylindrical dandruff at the base of the lashes and the presence of at least one alive demodex mites on eyelid margin by microscopy
2. Age >18 years.
3. Patients who can understand and follow the study instructions and can adhere to the scheduled follow-up plan.

The exclusion criteria consist of:

1. Patients who received previous treatment IPL or LLLT

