2. Poor compliance with eyelid scrubbing using tea tree oil (TTO)
3. Dead demodex mite on lash.
4. Contraindication of IPL: Skin Fitzpatrick scale V/VI, patients with pigmented lesions on the treatment area (Eyelid, Cheek).
5. Pregnancy or breastfeeding.
6. Active Skin disease: facial skin cancer, graft-versus-host disease, systemic lupus erythaematosus
7. Active eye infection: recurrent herpes simplex
8. Other lid disease ocular trauma, ocular deformity scar, exophthalmos, eyelid insufficiency
9. Patients with pigmented lesion on area of treatment.

We will use computer-generated random number allocation into 4 groups in a 1:1:1:1 ratio including seed number, with the outcome assessor blind and participant blind with allocation concealment:

- 1.) ShamLLLT + ShamIPL
- 2.) LLLT + ShamIPL
- 3.) IPL + ShamLLLT
- 4.) LLLT + IPL

***All groups receive mechanical with pharmacological treatment (Warm compression + Lid hygiene + 1% TTO) for 90 days with google form logbook for record compliance and prevent co-interventional treatments.

***All group with participant/investigator/interpreter blind.

Blinding and Allocation Concealment in Research Team:

1st Research Assistant : Allocates patients according to computer-generated random number allocation, ensuring allocation concealment, Evaluated VA , IOP , OSDI score by reads the questionnaire to the participant

2nd Research Assistant (The treatment administrator) : Administers IPL, LLLT, or sham treatments.

3rd Research Assistant : Conducts assessments using Keratograph and Lipiview2.

Main Researcher : Evaluates primary and secondary outcomes using case record forms, remaining blind to the treatment groups.

Intervention Description

Mechanical with pharmacological treatment : Warm compression 15 minutes + Lid hygiene + 1% TTO for 90 days

1%TTO : OCuSOFT Oust Demodex Eyelid Cleanser Foam Bottle 50ml (OCuSOFT, Richmond, TX) is the only commercially available medication in Thailand that contains 1% tea tree oil.

IPL : The Eye-light device (Espansione Marketing S.p.A., Bologna, Italy, waveleggths 1,200-1,500 nm, Delivery system 12cm²) (Thai FDA No 66-2-2-0012685) :

- Protective eye shields
- 5 flashes of light were applied for each eye (3 along the inferior orbital rim, 1 at the lateral canthus, and 1 applied horizontally along the inferior orbital rim)
- Therapeutic energy level (10–16 joules/ cm²) based on the degree of skin pigmentation.

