2nd-5th visit	
 - 1st – 4th week : Treatment session 1 per week x 4 weeks - 8th week : 1 month after treatment (2nd Data correction+Epilation)
6th visit	- 16 th week : 3 months after treatment(3 rd Data correction+Epilation)

All data will be collected using Microsoft Excel version 16.65 (Microsoft Inc, USA) and analyzed using SPSS Statistics.

Informed consent process: The study includes an informed consent (Board consent) process that allows the use of research data for future studies without the need for additional consent. . Data will be collected after this process and recorded by the investigator in a manner that subjects cannot be identified

Log book:

Provide a paper logbook to all participants to record compliance and prevent any potential co-intervention by patients or caregivers.

11. Data Analysis and Statistics

Sampling technique and Sample size: N=22 in each arm by

1-Way ANOVA Pairwise, 2-Sided Equality

$$n = 2\left(\sigma \frac{z_{1-\frac{\alpha}{2\tau}} + z_{1-\beta}}{\mu_A - \mu_B}\right)^2$$

$$1 - \beta = \Phi(z - z_{1-\alpha/(2\tau)})_+ \Phi(-z - z_{1-\alpha/(2\tau)}), z = \frac{\mu_A - \mu_B}{\sigma \sqrt{\frac{2}{n}}}$$

$$n = 2 \left(3.56 \frac{z_{1-\frac{0.05}{2\tau}} + z_{1-\beta}}{3.18 - 1.59} \right)^2$$

$$1 - \beta = \Phi(z - z_{1-\alpha/(2\tau)})_+ \Phi(-z - z_{1-\alpha/(2\tau)}), z = \frac{3.18 - 1.59}{3.56 \sqrt{\frac{2}{n}}}$$

n = Sample size (per pair) = 36, Each arm = 18, 20% drop out = 21.6 = 22 per arm

Φ = the standard Normal distribution function

Φ^{-1} = the standard Normal quantile function

α = Type I error, Significance level = 5%

β = Type II error, Power (1 - β): 80%

τ = the number of comparisons to be made = 6

Relative difference (δ) = 50% (or 0.50) by our expert opinion of minimal clinical significant difference

From previous study(28)

Standard deviation (σ) = Assume an estimated value based on available data or literature (28) = 3.56

(SD Demodex count at baseline)

$\mu_A = 3.18$

$\mu_B = 1.59$

Statistical analysis, plan, and data management

Demographic and baseline clinical characteristics will be presented as percentages for categorical data and as mean with standard deviation or median with interquartile range (IQR) for continuous data.

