Patients will benefit from receiving treatment for Demodex Blepharitis through eyelid scrubbing + 1% TTO (tea tree oil) and eyelid scrubbing + Low-Level Blue Light Therapy (LLLT) + Intense Pulsed Light (IPL) performed by specialized ophthalmologists. Volunteers will not receive any other benefits from participating in the research. All trial procedures will be tested by researchers and the team beforehand to identify potential issues. Safety will be paramount during the experiment, with basic first aid procedures in place and guidelines for referring participants in case of injuries or adverse effects

Justice:

Equitable Participant Selection: Justice demands fairness in participant selection, avoiding bias or discrimination. All eligible individuals should have an equal opportunity to participate, promoting inclusivity.

Researchers design the recruitment process to ensure diversity and representation across various demographics. The selection criteria based on scientific relevance, fostering inclusivity in the study population.

This research has clear inclusion and exclusion criteria, equally distributes risks and benefits, and employs a stratified study group allocation method.

Equitable Access to Benefits: The principle of justice extends to ensuring that the benefits resulting from the study are accessible to a broad population, preventing disparities in access to potential interventions.

Researchers proactively consider the implications of the study outcomes and work towards facilitating equal access to any effective interventions emerging from the trial, minimizing healthcare disparities.

Outcomes

Primary Outcome: Mean of Demodex Count - the number of Demodex mites per eyelash on a total of 4 collarettes lashes epilation per one eye in 30 days after end of treatment.

Secondary Outcomes:

- Mean of Demodex Count - the number of Demodex mites per eyelash on a total of 4 collarettes lashes epilation per one eye in 90 days after end of treatment.
- MGD Stage 1-5.

OSDI questionnaire used to evaluate ocular dry eye symptoms.

Meibum Quality.

Meibum Expressibility.

Telangiectasia grading: 0-3

- Surface Staining: NEI Grading System.
- LIPIMIEW used to measure Lipid Layer Thickness.
- The Keratograph 5M (OCULUS, Germany) used to measure noninvasive break-up time (NIBUT), tear meniscus height (TMH), % Meibomian Gland Loss (MGL)

13. Expected or Anticipated Benefit Gain

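### Section 12 says allocation is stratified, but no section names a factor, strata or blocks, and with 22 per arm a chance gap in entry mite count can exceed the effect sought

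*Combined protocol and SAP*

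**What the plan says.** Section 12 (Ethical Consideration, Justice) tells the ethics committee that the research "employs a stratified study group allocation method". It names no factor.

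Section 9 (Research Methodology) holds the only operational text: "We will use computer-generated random number allocation into 4 groups in a 1:1:1:1 ratio including seed number". Under the blinding arrangements, the first research assistant "Allocates patients according to computer-generated random number allocation, ensuring allocation concealment". Neither sentence mentions strata, blocks or minimisation, and neither does any other section.

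For entry, section 9 requires "the presence of at least one alive demodex mites on eyelid margin by microscopy" and sets no upper limit. The primary outcome in section 10 is the mean right-eye count at week 8, while the hypotheses in section 6 speak of a reduction in count. Visit 1, with its epilation, falls 0 to 14 days before treatment.

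Section 11 sizes the trial on six two-sided pairwise comparisons with an SD of 3.56, which it labels "SD Demodex count at baseline", and arrives at 22 per arm. Its analysis text names ANOVA for the image-based gland measures. It names no test for the mite count, no baseline covariate and no stratification factor.

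**The concern.** A list cannot be stratified unless a stratum is defined. A team that follows section 9 to the letter would not deliver what section 12 states.

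The gap matters more here than in many trials. The arms are small, entry is open to anyone from one live mite upward, and the SD (3.56) is larger than the larger mean used for planning (3.18). For a count that cannot be negative, that points to a long right tail, so a few heavily infested patients could fall in one arm. No adjustment for entry count is written, so nothing in the plan controls such a gap by design or by analysis. At stake are the precision of the pairwise comparisons and how believable the result looks beside an uneven baseline table.

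**Working it through.** **Inputs (section 11).** SD 3.56, labelled as the baseline SD; means 3.18 and 1.59, so the difference sought is 1.59; six comparisons at a two-sided 5% level; power 80%; 18 evaluable and 22 randomised per arm.

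**1. The plan's own figure.** The printed formula gives n = 2 × [3.56 × (2.638 + 0.842) / 1.59]² = 2 × 60.7 = 121.4, so 122 per arm. The plan states 36 per pair, hence 18 per arm, and 18 × 1.2 = 21.6, rounded to 22. The stated size is not reproduced. That is a separate matter; here 22 is taken as the planned arm size.

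**2. Chance gap in entry count without strata.** SE = 3.56 × √(2/n) and 95% range = ±1.96 × SE. The chance of a gap beyond 1.59 for one pair comes from the normal distribution. The chance for at least one of the six pairs comes from simulating four arm means one million times.

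| Comparison | SE | 95% range | One given pair | At least one of six pairs |
|---|---|---|---|---|
| 22 v 22 | 1.07 | ±2.10 | 13.9% | 44.9% |
| 18 v 18 | 1.19 | ±2.33 | 18.0% | 53.7% |
| 44 v 44 (factorial margin) | 0.76 | ±1.49 | 3.6% | not applicable |
| 122 v 122 (formula result) | 0.46 | ±0.89 | about 0.05% | not computed |

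For 22 v 22, 1.59 / 1.073 = 1.48, which gives 13.9%. A gamma-shaped count with mean 3.18 and SD 3.56 gives nearly the same: 13.6% and 43.6%.

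**3. How much reaches week 8.** An entry gap g shifts the expected week-8 difference by b × g, where b is the slope of the week-8 count on the entry count. If the SD is the same at both times, b equals the correlation. The documents do not give it, so I assume a range of 0.3, 0.5 and 0.7. A gap of 1.59 then carries 0.48, 0.80 or 1.11 into a comparison of week-8 counts. In an analysis of change from entry, the shift is (b − 1) × g, which is −1.11, −0.80 or −0.48.

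**4. Effect of two strata.** Assume a split at the median with arms balanced within each stratum. For the gamma shape the within-stratum SD is 2.64, so SE = 2.64 × √(2/22) = 0.80. The chance for a given pair falls to 4.6%, and for at least one pair to about 19%. For a normal shape the figures are 1.4% and about 7%, but a normal shape is less plausible here.

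**5. Effect of adjustment.** With the same three correlations, the residual SD is 3.56 × √(1 − ρ²) = 3.40, 3.08 or 2.54.

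**The case against.** The strongest reply is that randomisation needs no stratification to be valid. Chance imbalance averages to zero over repeated trials, and the ordinary standard error already allows for it. That stands: this is not a bias.

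It is also fair to say that the size of the gap comes largely from the arm size. At the 122 per arm that the plan's formula gives, a gap beyond 1.59 would be rare, and for the factorial margins it is already only about 4%. Both points stand. However, the trial is planned at 22 per arm and sized on pairwise comparisons.

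Third, adjustment for entry count would deal with the problem without touching the allocation. That is true, but none is planned.

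A reader might infer three stronger things that the documents do not support:

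- *That section 9 prescribes simple, unstratified randomisation.* It is silent on this. Under simple randomisation of 88 patients, some arm would start below 18 in roughly half of trials. A list fixed at 22 per arm fits the text equally well and never does this.
- *That any entry imbalance passes whole into the result.* This would need a slope of 1. The slope is not given, every arm receives the same lid treatment for 90 days, and a change-from-entry analysis, which the hypotheses suggest, would subtract the gap and often overcorrect.
- *That mite count was the intended stratum.* No section says so. The word may be loose wording in the ethics text.

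**Conclusion.** The point holds in a limited form. Sections 9 and 12 do not agree, and the stratification stated in section 12 cannot be carried out from the method as written.

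On the plan's own SD and arm size, a chance entry gap larger than the effect sought is an ordinary event for pairwise comparisons: about one trial in seven for a given pair, and a little under half for some pair. It is uncommon for the pooled margins. The consequence is lost precision and a baseline table that invites doubt.

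These figures assume that 3.56 applies to this trial's entry population and is on the same scale as the 1.59. The skew argument and the gamma figures also treat 3.18 as the mean of that same baseline count; section 11 labels the SD as baseline but does not label the mean. The gamma shape and the median split are assumptions. The probabilities describe the entry gap only. What reaches week 8 cannot be stated from the documents.

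**What to change.** **If enrolment has not begun** (section 9 gives November 2024 to November 2025): state in section 9 that randomisation is 1:1:1:1 in permuted blocks of randomly varying size, stratified by mean right-eye Demodex count at visit 1 (low or high, with the cut-point fixed before the first patient). Keep the seed and the concealment, and name the same factor in section 12.

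**In either case:** prespecify in section 11 that the analysis of the week-8 count adjusts for the visit-1 count, and for the stratum if one is used.

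**If enrolment has begun without strata:** remove the claim of stratification from section 12 and rely on the baseline adjustment.

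The cost is one regenerated list, a sentence in each of sections 9 and 12, and a line in section 11. The visit-1 epilation is already planned. The practical burden is that the count must be read and passed to the person who allocates before allocation takes place. The 0-to-14-day window leaves room for this, except where visit 1 and the first treatment fall on the same day. Two strata reduce the gap but do not remove it: some pair of arms would still differ by more than 1.59 in about one trial in five under the gamma shape. The adjustment is therefore needed even with strata.

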MGD Grade	Clear	Subclinical; nonobvious MGD; altered quality only on expression; no gland loss	Minimally altered quality of expressed meibum from scattered glands; None to minor gland loss	Mildly altered meibum quality; occasional lid margin signs; mild gland loss	Moderately increased opacity and viscosity of meibum; plugging; increased marginal vascularity; loss of orifice definition; moderate gland loss	Marked, diffuse MGD; cicatricial or noncicatricial; multiple lid margin signs; lid deformity and marked lid margin hyperaemia; Severe gland loss
Quality of expressed meibum grade range 0–3, LL, 8 glands, Range (0–24) [±]	0	1–5	6–10	11–15	16–20	21–24
Treatment of MGD based on symptoms and gland status	+ General advice about MGD, the potential influence of diet, home and work environment	+ Hygienic measures, heat and massage	+ Topical ATs	+ Oral tetracycline derivatives	+ Anti-inflammatory	
± Hygienic measures						
	± Emollient lubricant or liposomal spray					
	± Topical azithromycin					
	± Consider oral tetracycline derivatives					

This table should be read in conjunction with [Table 1](#), which provides a staging scheme for MGD-related *ocular surface disease*. Severity levels for each parameter are graded 1–5. A subclinical severity level has been introduced to accommodate asymptomatic MGD with normal lid margin features (nonobvious MGD) diagnosed only after gland expression. Note that this MGD scoring system does not provide a score for totally obstructed glands. Alternative systems for grading MGD exist and should be considered (see Appendices 5–7). Arita et al.¹ graded meibomian dropout in the combined upper and lower lids, using noninvasive meibography, with a scale range of 0–6 ([Table 3](#)). de Paiva et al.² used a composite system combining dropout, lid signs and meibum expressibility, with a scale range of 0–11 ([Table 3](#)). Korb and Black³ record the number of glands in a zone of 8, which yield a liquid excretion after standardized expression (MGD score 0–8). General treatment concepts, summarized here, are adapted from the Report on Management and Therapy. Recommended treatments are additive. At each clinical assessment, lack of response to treatment at the previous level moves treatment to the next level. ±, the decision to use this treatment is based on clinical judgment; +, treatment is recommended at this level. LL, lower lid; OSDI, Ocular Surface Disease Index.

[±]The increase in severity of MGD with increase in grade is denoted by a reduced quality of expressed meibum. Meibum quality (clarity and consistency) is assessed in eight glands of the central third of the lower lid on a 0–3 scale for each gland: 0 = clear; 1 = cloudy; 2 = cloudy with debris; 3 = thick, like toothpaste (total score range 0–24). ²

Figure1
